11.4. Determination of Sample Size

A total of 100 subjects with at least 48 weeks of CAM2038 exposure will be needed for the safety assessments. Approximately 228 subjects will be enrolled initially into this study with an estimated dropout rate of approximately 50% to ensure a total of 100 subjects are exposed to CAM2038. Once a total of 100 subjects complete 48 weeks of CAM2038 treatment, the study will be completed.

12. STUDY ADMINISTRATION AND INVESTIGATOR RESPONSIBILITIES

Additional details may be outlined in the Clinical Study Agreement (CSA) between the sponsor and the investigational site.

12.1. Regulatory and Ethical Considerations

12.1.1. Ethical Conduct of the Study

The Investigator will conduct the study in accordance with GCP and all applicable regulations, including, where applicable, the Declaration of Helsinki. The study will also be carried out in keeping with applicable national and local laws and regulations. This may include an inspection by the Sponsor's representatives and/or regulatory authority's representatives at any time.

12.1.2. Ethics Approval

The investigational site's IRB must meet all relevant regulatory requirements. The study protocol and ICF will be reviewed by the IRB prior to enrolling participants into the study; written approval from the committee must be received by the sponsor before drug will be released to the Investigator. The Investigator is responsible for submitting all protocol or ICF changes and SAE reports to the IRB according to local procedures. At a minimum, all SAEs requiring an investigational new drug safety report must be immediately reported.

In accordance with applicable local regulatory requirements, the Investigator may be obligated to provide periodic safety updates on the conduct of the study at his or her research site and notification of study closure to the IRB. Such periodic safety updates and notifications are the responsibility of the Investigator and not of the Sponsor. The Sponsor will be provided with copies of all notifications sent to the IRB.

All relevant correspondence from the IRB will be forwarded by the respective study site to the Sponsor in a timely fashion.

12.1.3. Subject Informed Consent

The Investigator (or authorized designee) will ensure that the participant (or the participant's legal representative) is given full and adequate oral and written information about the nature, purpose, potential and possible risks and benefits of the study. Each prospective subject will receive an IRB-approved ICF that summarizes the pertinent study information and will be given ample time to read the form and ask questions about the study. All information is to be provided in a language understandable to the participant and must not include any language that waives the participant's legal rights. Prospective participants must also be informed of their right to withdraw consent without prejudice at any time during the study. If the participant chooses to participate, he/she must sign the ICF before any study-related procedures are performed.

Significant changes to the protocol or product safety information may require a revision of the ICF, which must be reviewed and signed by all applicable study participants.

The time that informed consent is obtained must be documented. The Investigator must maintain the original, signed ICF in the participant's source documents. A copy of the signed ICF must be given to the study participant.

12.2. Privacy and Confidentiality

The Investigator is responsible for complying with applicable privacy regulations, per his or her jurisdiction. Only information identified in this protocol will be collected. The information collected will only be used for the purposes identified in this protocol.

To ensure anonymity and to limit disclosure, participants will be assigned a unique identifier at their first assessment. This identifier will be cross-referenced in the participant's chart. The identifier will not contain any potentially identifiable information. An identifier log will be maintained, linking each participant's name to the corresponding identifier. This log will be stored at the research site in a secure location.

The knowledge gained through this study is the property of the Sponsor. The Sponsor, representatives and affiliated companies of the Sponsor, the IRB, and regulatory agencies (such as the United States FDA) may inspect medical records related to the study to check the validity and accuracy of the data gathered in this study. Participant medical records (with participant's initials and/or date of birth) may be copied. Confidentiality of participant records will be maintained except where release of information is required by law.

The results of this study will be reported in such a manner that participants will not be identifiable in any way. Published reports or presentations will refer to grouped data or coded individual data and not to any identifiable individuals. Study reports sent to the Sponsor or drug regulatory agencies will not include participant names.

By signing the ICF, the participant consents to the collection, access, use, and disclosure of his or her information as described in the ICF document. If a participant withdraws consent, some of the subject's information may still be collected, used, and disclosed by those involved in this study, per applicable laws.

By signing this protocol, the Investigator affirms that he or she will maintain in confidence information furnished to him or her by the Sponsor and will divulge such information to his or her respective IRB or IEC under an appropriate understanding of confidentiality with such board. All data will be considered the sole property of the Sponsor. Please refer to the Clinical Study Agreement (CSA) for details.

12.3. Study and Site Closure

Upon completion of the study, all study data will be provided to the Sponsor following review of site study records for completeness, and data clarifications and resolutions. Accounting, reconciliation, and final disposition of used and unused study drugs, treatment codes, and emergency code break envelopes will be performed, as applicable.

In addition, the Sponsor reserves the right to temporarily suspend or prematurely discontinue this study at any time and for any reason. If such action is taken, the Sponsor will discuss this with

the Investigator (including the reasons for taking such action) at that time. The Sponsor will promptly inform any other investigators and/or institutions conducting the study, if the study is suspended or terminated for safety reasons and will inform the regulatory authorities of the suspension or termination of the study and the reason(s) for the action. If required by applicable regulations, the Investigator will inform the IRB promptly and provide the study participants with the reason for the suspension or termination. If the study is prematurely discontinued, all study data will be returned to the Sponsor.

12.4. Regulatory Documents and Records Retention

The Investigator is responsible for creating and/or maintaining all study documentation required by 21 CFR 50, 54, 56 and 312, ICH E6 section 8, as well as any other documentation defined in the protocol or CSA. The Investigator must provide key documents to the Sponsor prior to the start of the study. A complete list of required regulatory documents will be supplied by the Sponsor or its representative.

Federal and local regulations require that the Investigator retain a copy of all regulatory documents and records that support the data for this study for whichever of the following is the longest period of time:

- A period of 2 years following the final date of approval by the FDA or other regulatory agency of the study drug for the purposes that were the subject of the investigation; or
- A period of 5 years following the date on which the results of the investigation were submitted to the FDA or other regulatory agency in support of, or as part of, an application for a research or marketing permit for the study drug for the purposes that were the subject of the investigation.

The Sponsor will notify investigators once one of the above 2 timeframes has been satisfied.

If the investigation does not result in the submission of the data in support of, or as part of, an application for a research or marketing permit, records must be retained for a period of 2 years following notification by the Sponsor that the entire clinical investigation (not merely the Investigator's portion) is completed, terminated, or discontinued or 2 years following withdrawal of the Investigational New Drug application/Clinical Trial Authorization or request for marketing approval (New Drug Application/Marketing Authorization Application).

If the Investigator retires, relocates, or for other reasons withdraws from the responsibility of keeping the study records, custody must be transferred to a person who will accept the responsibility. The Sponsor must be notified in writing of the name and address of the new custodian. Study records should not be destroyed without consultation with the Sponsor.

12.5. Delegation of Responsibilities and Adequate Resources

The Investigator should have adequate time to conduct the study properly and should have an adequate number of qualified staff to assist with the conduct of the study.

The term “Investigator” used throughout this protocol refers to the principal investigator and/or qualified sub-investigators. However, the Investigator may delegate responsibilities to other investigational site personnel. The Investigator shall delegate tasks only to individuals qualified by education, training and experience to perform the delegated tasks. The Investigator shall have direct oversight of all delegated activities and shall document delegation of responsibilities. The Investigator is responsible for ensuring all delegated staff has been properly trained on the protocol and their assigned study responsibilities. A delegation log identifying all delegated duties and the individual to whom they have been delegated will be maintained at the investigational site.

12.6. Protocol Amendments

Approval of a protocol amendment by the Investigator’s IRB must be obtained before implementation of the protocol amendment, unless a change is necessary to eliminate an apparent immediate hazard to the participant or when the change involves logistical or administrative aspects of the study. The protocol amendment must be signed and dated by both the Sponsor and the Investigator. The Sponsor or designee will submit protocol amendments to the appropriate regulatory authorities, if required.

12.7. Financial Disclosure

Clinical investigators are required to provide financial disclosure information for the submission of certification or disclosure statements required under 21 CFR § 54. As defined in 21 CFR § 54.2, a clinical investigator is a listed or identified investigator or sub-investigator who is directly involved in the treatment or evaluation of research participants. The term also includes the spouse and each dependent child of the Investigator. In addition, investigators must promptly update financial disclosure information if any relevant changes occur during the course of the investigation and for 1 year following completion of the study.

1.0 DOCUMENT HISTORY

| Version | Date | Changes made since previous version |
|---------|-----------------|---|
| 1.00 | 25 January 2017 | Final |
| 1.01 | 20 April 2017 | Updates on the sample size and inclusion of separate analysis of subjects new to treatment. |

2.0 LIST OF ABBREVIATIONS

| Abbreviation | Definition |
|--------------|---|
| AE | Adverse Event |
| BPN | Buprenorphine or Buprenorphine/Naloxone |
| COWS | Clinical Opiate Withdrawal Scale |
| CRF | Case Report Form (may include electronic data capture systems or paper forms) |
| C-SSRS | Columbia-Suicide Severity Rating Scale |
| ECG | Electrocardiogram |
| MedDRA | Medical Dictionary for Regulatory Activities |
| mg | Milligram |
| PT | MedDRA Preferred Term |
| SAE | Serious Adverse Event |
| SAP | Statistical Analysis Plan |
| SC | Subcutaneous |
| SD | Standard Deviation |
| SL | Sublingual |
| SOC | MedDRA System Organ Class |
| SOWS | Subjective Opiate Withdrawal Scale |
| TEAE | Treatment-Emergent Adverse Event |
| VAS | Visual Analogue Scale |
| WPAI-GH | Work Productivity and Activity Impairment Questionnaire General Health |

3.0 INTRODUCTION

This statistical analysis plan (SAP) is based on Protocol HS-14-499, Version 3.0, dated 18-Nov-2016.

The purpose of this document is to provide details on study populations and on how the variables will be derived, how missing data will be handled, as well as details on statistical methodologies to be used to analyze the safety and efficacy data from the study.

The document may evolve over time, for example, to reflect the requirements of protocol amendments or regulatory requests. However, the final SAP must be finalized, approved by the Sponsor, and placed on file before the database is locked and treatment codes are unblinded. Deviations from the approved plan will be noted in the clinical study report.

4.0 STUDY DESCRIPTION

4.1 STUDY OBJECTIVES

Primary Objective: To demonstrate the safety and tolerability of CAM2038 products in 12-month (48-week) buprenorphine (BPN) treatment in adult outpatients with opioid use disorder.

Secondary Objectives: To evaluate efficacy of CAM2038 through several efficacy parameters, including urine toxicology, signs and symptoms of withdrawal and cravings in adult outpatients with opioid use disorder.

4.2 STUDY TREATMENTS

Following Screening, qualified patients will be initiated on either CAM2038 q1w or q4w, based on their current treatment status (qualified patients currently on sublingual (SL) BPN or seeking BPN treatment). Qualified patients will be initiated or transitioned to CAM2038 q1w or q4w as follows:

- Initiation of BPN treatment – initiate with CAM2038 q1w
- Currently receiving SL BPN treatments – transfer to corresponding CAM2038 q1w or q4w dose

Patients will be allowed to receive supplemental BPN during the study with booster SC injections of CAM2038 q1w 8 mg up to a maximum dose of 40 mg CAM2038q1w per week. For patients on CAM2038 q4w, a maximum of two booster doses of CAM2038 q1w 8 mg SC injections may be given per week. Dose adjustments (up or down titrations) will also be allowed at scheduled visits.

4.3 STUDY DESIGN

This is an open-label multi-center, 12-month safety study, consistent with standard practice for long-term safety studies. This one-year safety study will utilize CAM2038 q1w (once weekly) and CAM2038 q4w (once monthly) and will have 3 phases: Screening, Treatment, and Follow-up.

Patients who are currently taking SL BPN (weekly or monthly prescription visits) or individuals who are actively seeking BPN treatment but who have not yet begun a treatment regimen, may be eligible for the study.

Following Screening, qualified patients will be initiated on either CAM2038 q1w or CAM2038 q4w and receive study treatment as described in Section 4.3.

The study will end when at least 100 patients have been exposed to CAM2038 for 12 months (48 weeks). All patients will be transitioned back to usual care and followed for an additional 4 weeks (up to Week 53).

4.4 RANDOMIZATION AND BLINDING

This is an open-label study.

5.0 ANALYSIS POPULATIONS

5.1 OVERALL SAFETY POPULATION

All patients who received at least one dose of CAM2038.

5.2 FULL EXPOSURE SAFETY POPULATION

All patients who have been exposed to CAM2038 for 48 weeks.

5.3 EFFICACY POPULATION

In addition to the protocol-specified populations, the efficacy population will include all patients who have received at least one dose of CAM2038 and have provided some post-baseline efficacy measurements.

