7.0 SAMPLE SIZE

A total of 100 patients with at least 48 weeks of CAM2038 exposure will be needed for the safety assessments. Approximately 228 patients will be enrolled initially into this study with an estimated drop-out rate of 50% to ensure a total of 100 patients are exposed to CAM2038. Originally, the study was to end when at least 100 subjects had been exposed to CAM2038 for 12 months (48 weeks). However, a decision was made to allow all enrolled subjects to complete the entire treatment period and to not end the study after at least 100 subjects had completed 48 weeks of treatment.

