10.0 EFFICACY ANALYSES

10.1.1 EFFICACY VARIABLES

This is a long-term safety study and efficacy evaluation is not the primary objective of the study. All efficacy variables will be summarized using the efficacy population. The efficacy variables will include the following:

- Urine toxicology results for illicit opioids
- Self-reported illicit opioid use
- Retention (%) in treatment (identical to exposure)
- Retention (%) in study
- Measures of opioid withdrawal:
 - Clinical Opiate Withdrawal Scale (COWS)
 - Subjective Opiate Withdrawal Scale (SOWS)

- Measures of opioid craving:
 - Desire to Use Visual Analogue Scale (VAS)
 - Need to Use VAS
- Urine toxicology results for other drugs of abuse
- Work Productivity and Activity Impairment Questionnaire General Health (WPAI-GH)
- EQ-5D-5L Health Questionnaire
- Patient Satisfaction Scale

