10.1.4 RETENTION IN TREATMENT

Duration of treatment is defined as the time from the first dose of CAM2038 to the last dose plus 28 days if the last treatment was CAM2038 q4w or plus 7 days if the last treatment was CAM2038 q1w.

Duration of treatment will be summarized by the percentage of patients retained in treatment by week. Data will also be presented using Kaplan-Meier plots.

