10.1.5 RETENTION IN STUDY

Duration in study is defined as the time from first dose of CAM2038 to the date of study discontinuation.

Duration in study will be summarized by the percentage of patients retained in the study by week. Data will also be presented using Kaplan-Meier plots.

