11.1.1 EXTENT OF EXPOSURE

Summary statistics (number and percentage) of weeks of exposure to study drug (i.e. from the date of the first injection to the date of the last injection plus 28 days if the last treatment was CAM2038 q4w or plus 7 days if the last treatment was CAM2038 q1w) will be presented. Number of patients, number of

injections and exposure years will be presented by dose, treatment (CAM2038 q1w and CAM2038 q4w) and in total.

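### Retention tables and Kaplan-Meier plots leave out dosed patients with no post-baseline efficacy measurement; they should use all dosed patients

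*SAP*

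**What the plan says.** SAP 5.3 adds a third population to the two safety populations in the protocol. It consists of patients who "have received at least one dose of CAM2038 and have provided some post-baseline efficacy measurements". The Overall Safety Population in SAP 5.1 has no such condition: "All patients who received at least one dose of CAM2038".

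SAP 10.1.1 lists retention in treatment and retention in study among the efficacy variables and states: "All efficacy variables will be summarized using the efficacy population". Appendix A follows this. Tables 14.2.4.1 to 14.2.4.4, Tables 14.2.5.1 and 14.2.5.2, and Figures 14.2.1 and 14.2.2 are all labelled for the efficacy population.

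Neither retention definition uses an efficacy measurement. Under SAP 10.1.4, duration of treatment runs from first dose to last dose "plus 28 days if the last treatment was CAM2038 q4w or plus 7 days if the last treatment was CAM2038 q1w". Under SAP 10.1.5, "Duration in study is defined as the time from first dose of CAM2038 to the date of study discontinuation".

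SAP 10.1.1 also describes retention in treatment as the same thing as exposure. SAP 11.1.1 measures exposure by the same rule, "from the date of the first injection to the date of the last injection plus 28 days if the last treatment was CAM2038 q4w" (7 days for q1w), and Table 14.3.1.1 reports it on the Overall Safety Population.

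**The concern.** Retention should describe what happens to treated patients from their first dose. Here a patient enters the denominator only by coming back and being measured, and that later event is closely tied to the outcome. Protocol 7.1.2.3 takes efficacy measures at each weekly or monthly visit, so a dosed patient with none has almost certainly left early. Such patients are retention failures, and the plan can drop them from the retention analysis.

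Two things follow if anyone is excluded. Week 48 retention is overstated. And a duration that the SAP treats as identical to exposure appears on two denominators, all dosed patients for exposure and a subset for retention.

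A Week 48 figure for all dosed patients is within reach. SAP 7.0 records that "a decision was made to allow all enrolled subjects to complete the entire treatment period", so follow-up is not cut short when the hundredth patient reaches 48 weeks.

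**Working it through.** **Inputs**

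- N = 228 planned patients and about 50% dropout (SAP 7.0; Protocol 11.4). All 228 are assumed to be dosed.
- Expected number retained at Week 48: 228 × 0.5 = 114. The documents' minimum of 100 is used as a second case.
- k, the number dosed but without a post-baseline efficacy measurement, is not given. Values from 0 to 23 are assumptions.

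**The plan's own figure.** 100/(1 - 0.5) = 200, not 228. At 50% dropout, 228 gives 114 expected completers and a binomial probability of 0.973 of at least 100, against 0.528 with 200. The planned number is therefore a cautious one, and the present point does not depend on it.

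**Week 48.** No excluded patient is assumed to be still retained, so the numerator is unchanged and the denominator falls:

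reported retention = R/(N - k), against R/N on all dosed patients; ratio = N/(N - k).

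| k | k/228 | 114/(228 - k) | 100/(228 - k) | 228/(228 - k) |
|---|---|---|---|---|
| 0 | 0.0% | 50.0% | 43.9% | 1.000 |
| 4 | 1.8% | 50.9% | 44.6% | 1.018 |
| 5 | 2.2% | 51.1% | 44.8% | 1.022 |
| 11 | 4.8% | 52.5% | 46.1% | 1.051 |
| 23 | 10.1% | 55.6% | 48.8% | 1.112 |

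With 114 retained, a shift above 1 point needs 114/(228 - k) > 0.51, that is k > 228 - 114/0.51 = 4.47, so at least 5 patients.

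**Early weeks, retention in treatment.** The direction differs while an excluded patient still has credited time, because that patient then counts as retained and is missing from both numerator and denominator: (R - k)/(N - k). After a single q1w dose the credit is 7 days. Everyone has at least that much, so there is no effect in that window. A reversal in practice needs excluded patients who started on q4w (28 days of credit) while others have already ended. If 205 of 228 (89.9%) were retained at such a time and all k excluded patients were among them (assumptions), the reported values would be:

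- k = 5: 200/223 = 89.7% (-0.2 points)
- k = 11: 194/217 = 89.4% (-0.5 points)
- k = 23: 182/205 = 88.8% (-1.1 points)

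**Retention in study.** No credit applies, so the overstatement builds up from the excluded patients' study discontinuation dates.

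**By new-to-treatment status.** Group sizes are not given. If 0% to 5% of a group is excluded (assumption), a true 50.0% is reported as 50.0% to 50.0/(1 - 0.05) = 52.6%.

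**What is already planned on all dosed patients.** Table 14.3.1.1 gives exposure over time, and Table 14.1.1.1 gives completers and reasons for discontinuation. No Kaplan-Meier plot, weekly retention in study or retention by new-to-treatment status is planned on that population.

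**The case against.** The strongest reply is that little may be at stake. One post-baseline measurement on any instrument is enough for inclusion. New entrants return on Days 2 and 4, with withdrawal and craving scales possible on Days 2 to 7. Patients on q1w give urine and self-reports weekly. An early-termination visit could supply a measurement, and retention might itself be read as one. Exclusion is most plausible for q4w starters, whose first scheduled return is about Week 5, and their number is not stated. On this view k may be zero or a handful, and 23 is a stress value.

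The all-dosed picture is also partly there. SAP 8.1 reports the size of each population, so k can be read off and overall Week 48 retention converted by hand. Retention is an efficacy variable in the protocol, and one population for all efficacy outputs is consistent and clearly labelled. The endpoints are exploratory, and no test or decision rule rests on retention.

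Most of this stands as a limit on size, but it does not justify the population choice. The SAP does not define which measurements qualify, so k depends on how that condition is read, and Protocol 7.6 foresees patients who refuse termination procedures. A reader can convert one overall percentage by hand. The curves, weekly study retention and the new-to-treatment split cannot be recovered that way. Sharing a denominator with the urine and craving tables is a weak reason to accept an exclusion that depends on the outcome.

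**Conclusion.** The concern holds. The labels in SAP 10.1.1 and Appendix A are unambiguous, and the condition in SAP 5.3 can remove early leavers from an outcome that is computable for every dosed patient. At Week 48 any effect is upward. Its size cannot be fixed from the documents: nothing if no one is excluded, under 1 point for up to 4 exclusions, and 1.1 to 5.6 points for 5 to 23. These figures assume 228 dosed, 114 retained, and no excluded patient still on treatment at Week 48. The early-week reversal is small and rests on narrower assumptions. The primary safety objective is not affected. In an uncontrolled study, however, the descriptive percentage is itself the retention result, so its denominator should be right.

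**What to change.** In SAP 10.1.1, state that all efficacy variables except retention in treatment and retention in study use the efficacy population, and that both retention variables use the Overall Safety Population. In Appendix A, relabel Tables 14.2.4.1 to 14.2.4.4, 14.2.5.1 and 14.2.5.2 and Figures 14.2.1 and 14.2.2 to match. Retention in treatment then shares its denominator with exposure and no longer depends on which post-baseline measurements are taken to qualify.

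The cost is one sentence and eight population labels. No new data or method is needed, and the protocol defines no efficacy population that would stand in the way. There are two downsides: the Week 48 figure is slightly less favourable if anyone would have been excluded, and retention may then have a different denominator from the other efficacy tables, which a footnote can state.
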